4.4.2 Protocol Deviations

Important protocol deviations (IPD) are defined as those deviations from the protocol likely to have an impact on the perceived efficacy and/or safety of study treatments. The impact of IPD on the efficacy and/or safety results will be investigated by assessing the robustness of the study results and conclusions to the choice of analysis set, both including and excluding data potentially affected by IPD.

This evaluation will be performed on a Blind Data Review Meeting (BDRM) shortly before database lock/unblinding. Results and population assignments will be summarised in a BDRM report which will be signed off by all relevant scientific experts.

Important protocol deviations and any action to be taken regarding the exclusion of subjects or affected data from specific analyses are defined in the project-specific Protocol Deviation Specification. The IPD will be summarised for each study part by treatment group (each dose level of AZD1402, placebo, and pooled AZD1402), and overall.

The IPD include the following:

- Inclusion/exclusion criteria deviations.
- Treatment deviations.
- Visit out of window.
- Subjects receiving prohibited concomitant medications.
- Procedures not performed or out of window.

By-participant listings of IPD will be provided.

4.5 Analysis Sets

A summary of the number and percentage of subjects included and excluded from each analysis population will be presented by treatment group and overall, for each part of the study.

A by subject listing of analysis set details should be provided. This listing should be presented by treatment group and should include subject identifier, exclusion flag for each population, and reason for exclusion from each analysis set. All subjects randomised should appear in this listing.

A BDRM will be held before opening randomisation codes in order to assign the subjects to the different analysis populations according to the specified definitions. The precise reasons for excluding subjects from the study populations will be fully defined and documented in the BDRM Report.

4.5.1 Safety Set

The Safety set (SS) will include all participants who are randomised and received any study intervention.

Participants are evaluated according to the actual treatment they received.

If a participant received a different treatment dose than randomised throughout the study, they will be analysed according to treated dose, not the randomised dose. If a participant received study intervention from the wrong kit for only part of the treatment duration, they will be analysed according to their randomised dose.

The SS will be used for all safety analyses.

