4.4.1 Premature Termination of the Study and Stopping Criteria

The Sponsor will suspend or terminate a dose level or the entire study (as applicable) following the review of all available safety data if any of the following occurs at the dose or study level:

Per dose level (Part 1)

- Two participants experience a FEV₁ drop $\geq 30\%$ from baseline (in-clinic)* attributable to AZD1402.
- One participant experiences a hypersensitivity-like SAE attributable to AZD1402.

- Day 28 exposure in one participant in Part 1 exceeds or is predicted to exceed (for Part 1b) a peak concentration Cmax of 5420 ng/mL or exposure AUC(0-24 h) of 68700 ng.h/mL.

*Baseline Part 1: Mean of Day -1 and Day 1.

Per dose level (Part 2)

- Clinically significant FEV₁ decline from baseline* attributable to AZD1402 comparing the number of participants reaching a FEV₁ drop $\geq 30\%$ in active versus placebo as assessed by the DSMB.
- One participant experiences a hypersensitivity-like SAE attributable to AZD1402.

*Baseline Part 2: Mean of Day 1 (15 minutes and 45 minutes pre-dose).

Study level

- Two participants experience a hypersensitivity-like SAE and/or severe hypersensitivity event attributable to AZD1402.
- The overall safety and tolerability profile as determined by the DSMB does not justify continuation with dosing as per the current protocol.
- Significant immunogenicity impacting safety and tolerability.
- The Sponsor considers the applied doses of the study intervention to be no longer relevant.
- The Sponsor decides to discontinue the study.
- Data not known before, become available and raise concern about the safety of AZD1402 so that continuation would pose potential risks to the participants.

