9.3 Populations for Analyses

The following populations are defined:

Table 7 Populations for Analysis

Population/Analysis set	Description
Enrolled	All participants who sign the informed consent form.
Full Analysis Set (FAS)	All participants who are randomised and received any study intervention. Participants are evaluated according to the treatment assigned at randomisation. The FAS will be used for all analyses of demographic baseline characteristics and efficacy data.
Per Protocol Set (PPS)	A subset of the FAS consisting of all participants who do not violate the terms of the protocol in a way that may affect the primary efficacy endpoint significantly. All decisions to exclude participants from the PPS will be made and documented prior to the unblinding of the study.
Safety Set (SS)	All participants who are randomised and received any study intervention. Participants are evaluated according to the actual treatment they received. If a participant received a different treatment dose than randomised throughout the study, they will be analysed according to treated dose, not the randomised dose. If a participant received study intervention from the wrong kit for only part of the treatment duration, they will be analysed according to their randomised dose. The SS will be used for all safety analyses.
Pharmacokinetic (PK) set	All participants in the SS who have detectable PK data and with no major protocol deviations considered to impact on the analysis of PK data. The exclusion of any participants or timepoints from the calculation of the PK parameters will be documented by the PK scientist including the reason(s) for exclusion prior to the unblinding of the study. The available concentration data and PK parameter data for any participants excluded from the PK analysis set will be listed only, and presented in the individual figures of concentration-time plots. The PK analysis set will be used for all PK analyses.
Immunogenicity set	All participants in the SS with at least one post-treatment ADA result (positive or negative) with exception for any analysis of relationship of

Population/Analysis set	Description
	ADA with PK where the immunogenicity set will instead include all participants in the PK set. The immunogenicity analysis set will be used for all ADA analyses.

Abbreviations: ADA = anti-drug antibody; FAS = full analysis set; PPS = per protocol set; PK = pharmacokinetics; SS =safety set

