4.5.4 Immunogenicity Set

The Immunogenicity set (IS) will include all participants in the SS with at least 1 post-treatment ADA result (positive or negative), with exception for any analysis of relationship of ADA with PK where will instead include all participants in the PK set.

The immunogenicity analysis set will be used for all ADA analyses.

All the immunogenicity parameters and listings will be based on the IS and presented for each treatment group.

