4.17 Safety Evaluation

All safety summaries and analyses will be based upon the SS as defined in Section 4.5.1 and will be presented by dose level of AZD1402, pooled AZD1402, and placebo and by study part.

In general, there will be no imputation of missing data for the safety analyses. All safety data (scheduled and unscheduled) will be presented in the data listings.

Baseline for safety evaluations will be the last value obtained before first study intervention.

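### The partial wrong-kit rule in the Safety Set keeps a placebo participant who inhaled AZD1402 in the placebo group for adverse events, FEV1 falls and antibody results

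*SAP*

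**What the plan says.** The Safety Set is everyone randomised who took any study intervention. Protocol Table 7 (section 9.3) gives the principle for this set: "Participants are evaluated according to the actual treatment they received". SAP 4.5.1 repeats it. Both documents then give two rules for dosing errors:

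- **Wrong dose for the whole study.** If a participant "received a different treatment dose than randomised throughout the study, they will be analysed according to treated dose".
- **Wrong kit for some of it.** If someone "received study intervention from the wrong kit for only part of the treatment duration, they will be analysed according to their randomised dose". Protocol Table 7 has the same rule: "wrong kit for only part of the treatment duration, they will be analysed according to their randomised dose".

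Neither document separates a placebo participant given AZD1402 from an AZD1402 participant given placebo.

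The assignment carries forward. SAP 4.17 states: "All safety summaries and analyses will be based upon the SS as defined in Section 4.5.1". SAP 4.5.4 builds the Immunogenicity Set from "all participants in the SS with at least 1 post-treatment ADA result", reports it by treatment group and gives it no assignment rule of its own. Protocol 4.1.2 has ADA samples taken from all participants in both parts, so the placebo group has ADA results to report.

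**The concern.** The second rule reverses the principle it sits under. A safety comparison with placebo needs a control group that has not been exposed to the drug. Under this rule, a placebo participant who inhaled AZD1402 for some of the four weeks and then has a respiratory event, an FEV1 fall or a new antibody response is counted against placebo, and nothing is counted against the dose that was taken. For any event the drug caused, the placebo rate goes up and the active rate stays too low. The error therefore favours the drug.

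Partial exposure cannot be set aside as harmless here. Protocol 2.3.1 reports hypersensitivity-like events in an earlier study with intermittent dosing, and an antibody response is a question about any exposure. In Part 1, safety is the primary objective and the placebo groups are very small.

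**Working it through.** No stated figure in the plan depends on this rule, so there is none to reproduce apart from the dose count.

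**1. How much wrong dosing counts as part of treatment.** Dosing is twice daily for 27 days with one dose on Day 28: 27 × 2 + 1 = 55, which agrees with SAP 4.9.2. Anything short of all 55 is only part, so the rule covers 1 to 54 wrong doses, or 1/55 = 1.8% to 54/55 = 98.2% of planned dosing.

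**2. Where errors can enter in Part 2.** The schedule of activities has drug dispensed at Visit 3 (Day 1) and Visit 5 (Day 14). There are 13 × 2 = 26 doses before Day 14 and 55 − 26 = 29 from Day 14. If a whole dispensing were wrong (an assumption), it would cover 26/55 = 47% or 29/55 = 53% of doses. Either counts as partial and goes back to the randomised group. To reach the treated-dose rule, both dispensings would have to be wrong.

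**3. Size of one case.** Planned placebo numbers are 30/3 = 10 in Part 1a (1:1:1), 15/3 = 5 in Part 1b (2:1) and 80 in Part 2. One misassigned participant with an event, or with a positive ADA result, adds 1/n to the placebo rate:

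| Placebo group | n | 1/n |
|---|---|---|
| Part 1a | 10 | 10 points |
| Part 1b | 5 | 20 points |
| Part 1 pooled | 15 | 6.7 points |
| Part 2 | 80 | 1.25 points |
| Part 2, if the sample size is raised to the maximum in protocol 9.5 | 107 | 0.93 points |

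**4. Before and after, Part 2.** Suppose this is the only event and the drug taken was the dose with 80 participants. Under the current rule placebo is 1/80 = 1.25% and active is 0/80. Assigned by exposure, placebo is 0/79 and active is 1/81 = 1.23%. Active minus placebo moves from −1.25 to +1.23 points, so its sign changes.

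**5. Whether anything else in the SAP recovers the case.**

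- SAP 4.4.2 says results will be examined with and without data affected by important deviations and across analysis sets. The Safety Set and the FAS have the same members, and for a partial kit error they put the participant in the same group, so comparing them shows nothing. SAP 4.20 removes the per-protocol analysis, and no safety or ADA sensitivity table is specified.
- SAP 4.17.1 assigns a repeated adverse event to the study drug of the period in which it first occurred. That is a different principle from SAP 4.5.1, and the two need reconciling.
- The ADA-with-PK analysis uses the PK set, so the point concerns the main ADA summaries.

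**The case against.** The rule is prespecified, is the same in both documents, and matters only if a kit error happens. Several safeguards make an error less likely or easier to see. Kits are allocated by IRT (protocol 6.3), and clinic doses are confirmed by a second staff member (protocol 6.4). Wrong treatment is an important deviation, summarised by group and listed by participant (protocol 9.4.1, SAP 4.4.2). Dosing is listed by subject (SAP 4.9.1). Placebo samples can be assayed to confirm treatment (protocol 8.5.1.3). A separate deviation specification, not among these documents, may say more. After a very short exposure, keeping the randomised group is less clearly wrong.

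All of that stands as mitigation. It makes a case traceable, but it does not change the group in which the summary tables count it. Detection is also not assured: Appendix B 4 exempts IRT-caused errors from medication-error reporting, and placebo PK samples are not assayed routinely.

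Two stronger readings are tempting, and the documents support neither.

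- A reader might infer that the rule can hide a stopping event, because one criterion in protocol 4.4.1 is "One participant experiences a hypersensitivity-like SAE attributable to AZD1402". That criterion turns on the attribution of an individual case after review of all available safety data, with unblinded committees overseeing both parts. A placebo participant who took AZD1402 can still meet it. The other Part 2 criterion compares active with placebo on the number of participants with FEV1 falls of 30% or more, so it would be sensitive to group labels if the DSMB outputs follow the Safety Set rule. The documents do not say whether they do.
- A reader might infer that one wrong kit means two weeks on active drug. The kit description in protocol Table 5 is partly redacted, and the number of kits per dispensing is not given, so exposure per wrong kit cannot be derived. The supported range is 1 to 54 doses.

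**Conclusion.** The point holds as a flaw in a stated rule. The Safety Set is declared to follow actual treatment, yet a placebo participant with any partial exposure to AZD1402 is reported as placebo for safety and, by inheritance, for ADA. For drug-related events the bias favours the drug.

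The size is conditional. Each such case with an event is worth 1.25 points of the Part 2 placebo rate, 10 points in Part 1a and 20 in Part 1b. These figures use planned group sizes and assume that the error occurs and that the participant has the event in question. The documents give no kit-error rate, so no expected bias can be stated, and nothing in them suggests that an error has happened. The case for changing the rule is that the change is cheap and is better made before unblinding than after a case appears.

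**What to change.** In SAP 4.5.1 and protocol Table 7, replace the partial wrong-kit sentence, for the Safety and Immunogenicity Sets only, with text to this effect:

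> A participant randomised to placebo who received at least one dose of AZD1402 is summarised in the AZD1402 group for the dose received. A participant randomised to AZD1402 who received some placebo stays in the AZD1402 group. A participant who received more than one AZD1402 dose level is summarised under a prespecified level (for example, the highest received). Each case is footnoted, and the dates of wrong-kit use are listed.

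SAP 4.5.4 should say that it uses this assignment, and the adverse event counting text in SAP 4.17.1 should be brought into line with it. The FAS stays as randomised.

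The cost is a few sentences in each document and a treatment flag in the analysis datasets. SAP section 1 allows changes before database lock through a new version. The drawback is that events before the wrong kit was used also move to the AZD1402 group. That is conservative, and the footnotes and listed dates let a reader identify those events.

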4.5.2 Full Analysis set

The Full analysis set (FAS) will include all participants who are randomised and received any study intervention.

Participants are evaluated according to the treatment assigned at randomisation.

The FAS will be used for all analyses of demographic baseline characteristics and efficacy data.

4.5.3 Pharmacokinetic Set

The Pharmacokinetic set (PKS) set will include all participants in the SS who have detectable PK data, and with no major protocol deviations considered to impact on the analysis of PK data.

The exclusion of any participants or timepoints from the calculation of the PK parameters or statistical analysis will be documented by the PK scientist including the reason(s) for exclusion prior to the unblinding of the study. The available concentration data and PK parameter data for any participants excluded from the PK analysis set will be listed only and presented in the individual figures of concentration-time plots.

The PK analysis set will be used for all PK analyses. For the SRCs at completion of Part 1a before progressing to Part 1b/2a and from Part 1b before progressing to Part 2b the protocol deviations for the PK set will not be evaluated.

4.5.4 Immunogenicity Set

The Immunogenicity set (IS) will include all participants in the SS with at least 1 post-treatment ADA result (positive or negative), with exception for any analysis of relationship of ADA with PK where will instead include all participants in the PK set.

The immunogenicity analysis set will be used for all ADA analyses.

All the immunogenicity parameters and listings will be based on the IS and presented for each treatment group.

4.6 Demographics and Baseline Characteristics

Analyses of demographic and baseline characteristics will be performed on the FAS.

Demographic characteristics to be assessed are age (years), sex, race, ethnic group and country. Age groups 18 to 64, 65 to 75 will also be presented (for EudraCT reporting).

For demography, height/weight baseline is defined as the assessment on screening

Participant baseline characteristics to be assessed are height (cm), weight (kg), BMI (kg/m²), CRP (mg/L) and Eosinophils count (10⁹ /L), and smoking history.

Asthma characteristics at baseline will include: time since asthma diagnosis, time since last exacerbation, number of exacerbations and most recent exacerbation type in the 12-month period preceding the subject enrolment in the study.

- Time since asthma diagnosis (years) is calculated as follows:
(Asthma diagnosis date-Screening date/Re-screening date) /365.25
- Time since last exacerbation (days) is calculated as follows:
(Last exacerbation date- Screening date/Re-screening date) + 1

For missing day and/or month the following strategy will be followed:

- Initial asthma diagnosis date/last exacerbation date with valid year and month but missing day:
Such a date will be assumed at the 15th of the month in the Year.
- Initial asthma diagnosis date with valid year but missing month and day:
Such a date will be assumed at the 15th of June in the Year,

Baseline lung function data to be assessed for Part 1 include:

- In-clinic pre-bronchodilator FEV₁ and FVC in absolute value (L) and percent of predicted values (% PN).
- In-clinic pre-bronchodilator ratio FEV₁/FVC (%).
- Home assessment pre-bronchodilator spirometry absolute values of FEV₁ (L).
- In-clinic FeNO (part per billion [ppb]) (geometric mean and geometric coefficient of variation [GeoCV (%)] will be presented instead of mean and SD for this variable).
- FeNO at home assessment (ppb) (geometric mean and GeoCV [%] will be presented instead of mean and SD for this variable).

Statistical Analysis Plan

Lung function and reversibility data at screening to be assessed for Part 2 include:

- In-clinic pre-bronchodilator FEV₁ and FVC in absolute value (L) and percent of predicted values (% PN).
- In-clinic pre-bronchodilator ratio FEV₁/FVC (%).
- Home assessment pre-bronchodilator spirometry absolute values of FEV₁ (L).
- In-clinic post-bronchodilator FEV₁ and FVC in absolute value (L) and percent of predicted values (% PN).
- In-clinic post-bronchodilator ratio FEV₁/FVC (%).

Baseline lung function data to be assessed for Part 2 include:

- In-clinic FEV₁ in absolute value (L)
- In-clinic FeNO (part per billion [ppb]) (geometric mean and geometric coefficient of variation [GeoCV (%)] will be presented instead of mean and SD for this variable).

Baseline diary data to be assessed for **CC1** Part 2 include:

- ACQ-6 score

Baseline diary data to be assessed for Part 1 include:

- Cough VAS (mm)

Baseline diary data to be assessed for Part 2 include:

- Morning PEF (L/min).
- Evening PEF (L/min).
- Daily asthma symptom score.

The daily values of rescue medication use and of asthma symptom scores are calculated as the mean of the evening measurement for day n and the morning measurement for day n + 1.

Additional baseline assessments to be assessed for Part 1 and Part 2 include:

- Eosinophils count (10⁹/L).
- hsCRP (mg/L).

Additional baseline assessments to be assessed for Part 2 include:

- Eosinophils count group (cells/ μ L): < 300, \geq 300.

The baseline assessments detailed above will be summarised by treatment group (each dose level of AZD1402, placebo, and pooled AZD1402) and overall.

By-participant listings of demographics, participants characteristics, asthma history will be provided for the randomised subjects. For weight, height and BMI, and asthma exacerbation the listings will be presented for the safety set. All listings will be presented for each study Part.

4.6.1 Baseline, Change from Baseline and Percentage Change from Baseline Definitions

In general, the baseline which will be used in calculation of change from baseline will be the last value obtained before first study intervention.

Exceptions to the general definition of baseline (for calculation of change from baseline) are the following:

- In-clinic FeNO test: baseline is defined as the mean of measurements at Day -1 and at Day 1 morning pre-dose at Visit 3 in Part 1 and as Day 1 morning pre-dose at Visit 3 in Part 2.
- FeNO at home assessments: baseline is defined as the mean of all available measurements during the 7 days period prior to Day 1 in Part 1.
- In-clinic pre-bronchodilator FEV₁, FVC and FEV₁/FVC in absolute values and in percent of predicted values: baseline for Part 1 is the mean of measurements at Day -1 and at Day 1 morning pre-dose at Visit 3; for Part 2 is the pre-bronchodilator assessment at Visit 1.
- In-clinic FEV₁ is the mean of Day -1 and Day 1 morning pre-dose at Visit 3 for Part 1 and is the mean of measurements at Day 1 pre-dose timepoints (15 and 45 minutes pre-dose) for Part 2.
- In-clinic post-bronchodilator FEV₁, FVC and FEV₁/FVC in absolute values and in percent of predicted values: baseline is the measurement at Visit 1 (1 measurement) within performed 15 to 30 minutes after inhalation of 400 µg of salbutamol.
- FEV₁ home spirometry: baseline is defined as the mean of all available measurements during the 7 days period prior to Day 1 in both Part 1 and Part 2. i.e. The baseline for the morning assessments will be: the mean of all available morning measurements in the 7 days period prior to Day 1. Same approach will be used for the baseline for the evening assessments.
- e-Diary variables (cough VAS, **CCI** [REDACTED], evening PEF, daily asthma symptom score): baseline is average over measurements on the 7 days prior to randomisation. For the morning assessments of PEF, daily use of rescue medication and asthma symptoms the baseline is average over morning assessments from Day -6 to Day -1 and the Day 1 pre-dose assessment.

For e-Diary any study day will be derived relative to randomisation.

In case of missing values among the measurements defining the baseline of the e-Diary variables, the baseline will be defined as the mean of all available measurements in the 7 days period. In all other cases of missing values in measurements defining a baseline, the baseline value will be defined as the last non-missing value prior to Day 1.

Change from baseline will be defined as the value post-dosing minus the baseline defined, for each timepoint.

Percent change from baseline will be calculated as:

- Percent change from baseline = ((visit value – baseline value)/baseline value) ×100%

The average change from baseline over the treatment period will be calculated from the subjects' average measurements of all assessments performed while subjects are on-treatment, minus the baseline value.

If either a visit value or the baseline visit value is missing, the absolute change from baseline value and the percent change from baseline will also be set to missing.

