9.4.2.1 Primary Endpoint

The primary efficacy endpoint for Part 2 (Main Cohort) is the change from baseline in pre-bronchodilator FEV₁ at Week 4 compared to placebo.

The change from baseline in FEV₁ will be analysed using MMRM with treatment group, week (1 to 4), country, eosinophil count group (< 300, \geq 300 cells/ μ L), baseline FEV₁, and treatment-by-week interaction as fixed effects with participant as random effect. In this model, Week 1 to 4 corresponds to Visit 4 to 7. The within-participant correlation will be modelled using the unstructured covariance matrix. The Kenward-Roger approximation will be used to estimate the degrees of freedom.

Baseline for FEV₁ will be defined as the mean of the 2 measured values before first study intervention administration (30 minutes apart, at -45 minutes and -15 minutes, before study intervention) on Day 1.

Besides the main analysis in the FAS, treatment effect in primary endpoint will be evaluated in subgroups defined by measurements of eosinophil count (< 300 and \geq 300 cells/ μ L), and of FeNO (< 50 and \geq 50 ppb) evaluated at Day 1 pre-dose.

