4.11 Primary Efficacy Variable (Part 2)

The primary variable for the assessment of efficacy for Part 2 is the change from baseline pre-bronchodilator in-clinic FEV₁ at Week 4.

The change from baseline in pre-bronchodilator FEV₁ will be analysed using MMRM with treatment group, week (1 to 4), country, baseline FEV₁, and treatment-by-week interaction as fixed effects and with participant as random effect. In this model, Week 1 to Week 4 corresponds to Visit 4 to Visit 7.

The within participant correlation will be modelled using the unstructured covariance matrix. The Kenward-Roger approximation will be used to estimate the degrees of freedom. The REML method will be applied.

If the estimating algorithms will not converge, the following steps will be taken to simplify the model until convergence is achieved:

1. As a first step, try in order these 3 covariance structures: Toeplitz, the first-order autoregressive, and compound symmetry. Stop as soon as convergence is achieved.

Statistical Analysis Plan

2. If step 1 does not work, the treatment-by-week interaction will be removed from the last model in step 1, ie, from the model with compound symmetry.
3. In case non-convergence persists, the analysis will be changed to use the analysis of covariance (ANCOVA) instead of mixed-effects model for repeated measures.

Each treatment effect and treatment comparisons (all active treatments to placebo) will be estimated by the Least Square means (LS means) and the difference in LS means at the corresponding week (Week 1, Week 2, Week 3, Week 4) on the treatment-by-week interaction, along with their standard errors (SE) and 95% CIs, and the p-value corresponding to the between-treatment group difference. A plot showing the LS mean change (+/- SE) from baseline in FEV₁ over time within each treatment group will be provided.

Missing values will not be imputed. In this analysis it is thus assumed that any missing FEV₁ values are missing at random.

A listing of the primary efficacy data will be provided based on the FAS.

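### SAP 4.6.1 lists two Part 2 baselines that both fit in-clinic pre-dose FEV₁, gives Part 2 FVC only a Visit 1 baseline, and its missing-value rule, read literally, discards a valid Day 1 reading

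*SAP*

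**What the plan says.** SAP 4.6.1 lists exceptions to the general last-pre-dose baseline and states that they are for computing change from baseline. Four of its rules matter here.

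- **In-clinic pre-bronchodilator FEV₁, FVC and FEV₁/FVC:** the baseline "for Part 2 is the pre-bronchodilator assessment at Visit 1".
- **In-clinic FEV₁:** the baseline "is the mean of measurements at Day 1 pre-dose timepoints (15 and 45 minutes pre-dose) for Part 2". FVC is not named.
- **Missing components, e-Diary variables:** "the baseline will be defined as the mean of all available measurements in the 7 days period".
- **Missing components, everything else:** "the baseline value will be defined as the last non-missing value prior to Day 1".

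The home FEV₁ bullet already uses "the mean of all available measurements during the 7 days period prior to Day 1 in both Part 1 and Part 2", and the home FeNO bullet (Part 1) works the same way.

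Elsewhere, SAP 4.11 states: "The primary variable for the assessment of efficacy for Part 2 is the change from baseline pre-bronchodilator in-clinic FEV₁ at Week 4". Protocol 9.4.2.1 states: "Baseline for FEV₁ will be defined as the mean of the 2 measured values before first study intervention administration", at 45 and 15 minutes pre-dose on Day 1. SAP 4.17.5 plans tables of absolute value, change and percentage change for in-clinic FEV₁, and similar tables for FVC. SAP 4.17 sets a general last-pre-dose baseline for safety evaluations and does not say whether the 4.6.1 exceptions apply.

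**The concern.** There are three separate faults in one section.

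1. **FEV₁.** Two listed exceptions give different Part 2 baselines for what is, in this trial, the same measurement. SAP 4.11 calls the primary variable both pre-bronchodilator and in-clinic, so both fit, and only the Visit 1 bullet carries the word pre-bronchodilator. Preferring the specific rule over the general one does not help, because both are specific.
2. **FVC.** No Day 1 bullet covers it. A programmer following 4.6.1 would measure Part 2 FVC change from screening, and one following 4.17 would measure it from Day 1.
3. **Missing readings.** The non-diary rule is triggered by any missing component and looks only before Day 1. In Part 2 it can replace a valid Day 1 FEV₁ with the Visit 2 value. In Part 1, a missing Day -1 value does the same to a valid Day 1 pre-dose FEV₁, FVC or in-clinic FeNO.

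The SAP Introduction says the document serves as the programming specification, so its text should settle these points. The third fault reaches the primary model, where baseline FEV₁ enters both the response and a covariate.

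**Working it through.** The plan states no figure on this point to reproduce. The check compares the text, then works out timing and size.

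**Which FEV₁ baseline is intended.** Protocol 9.4.2.1 uses the two Day 1 readings, 4.1.2 uses Visit 3, and 4.4.1 and 7.1.1 use the Day 1 mean. SAP 4.6 separates a Part 2 screening table (pre- and post-bronchodilator FEV₁ and FVC) from a Part 2 baseline table (in-clinic FEV₁ and FeNO). The Visit 1 clause probably belongs to the screening table. SAP 4.20 declares no change of baseline. Day 1 is intended.

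**Timing** (Protocol Table 2 and footnotes; no Day 0). Visit 2 is at Day -28 ± 2, which is 26 to 30 days before Day 1. Visit 1 is up to 14 days earlier, or 28 if extended.

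- Shortest: just over 26 days, with Visit 1 immediately before Visit 2.
- Nominal: 28 + 14 = 42 days (Week -6).
- Longest: 30 + 14 = 44 days, or 30 + 28 = 58 if screening is extended. Protocol section 5 also lets run-in be extended, with no limit stated.

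**FVC tables** (values assumed). Day 1 is 3.0 L and Week 4 is 3.1 L.

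| Baseline used | Change | Percentage change |
|---|---|---|
| Day 1, 3.0 L | +100 mL | 0.1/3.0 = 3.3% |
| Visit 1, 2.9 L | +200 mL | 0.2/2.9 = 6.9% |
| Visit 1, 3.1 L | 0 mL | 0.0% |

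A mean drift between Visit 1 and Day 1 moves every within-arm change by that amount, on average equally in all arms.

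**Missing-value rule, one patient** (values assumed). Visit 2 is 2.05 L, the Day 1 reading at -45 min is missing, the reading at -15 min is 2.20 L, and Week 4 is 2.30 L. The literal rule gives 2.30 − 2.05 = +0.25 L. The available Day 1 reading gives 2.30 − 2.20 = +0.10 L.

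**Missing-value rule, primary analysis.** With baseline as a covariate, the cost is in residual variance. Take Week 4 alone as an approximation to the MMRM, equal variances and one slope. Let *f* be the share lacking one Day 1 reading, and let *rm*, *r1* and *rv* be the correlations with Week 4 of the Day 1 mean, one Day 1 reading and Visit 2. The variance ratio, literal rule over available reading, is

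R = {1 − [(1−f)·rm + f·rv]²} / {1 − [(1−f)·rm + f·r1]²}

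For 0.85/0.84/0.75 and f = 10%: (1 − 0.840²)/(1 − 0.849²) = 0.2944/0.2792 = 1.054.

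| rm / r1 / rv (assumed) | f = 1% | f = 5% | f = 10% |
|---|---|---|---|
| 0.90 / 0.89 / 0.89 | 1.000 | 1.000 | 1.000 |
| 0.90 / 0.89 / 0.85 | 1.004 | 1.019 | 1.037 |
| 0.85 / 0.84 / 0.75 | 1.006 | 1.027 | 1.054 |

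A simulation of 2,000,000 patients agrees to within 0.001. As patients per arm at the planned 80, 80 × (1 − 1/R) in the last row is about 0.4, 2.1 and 4.1.

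**The case against.** The strongest reply is that the FEV₁ conflict is one of labels. The two bullets give the same Part 1 rule, their wording follows the screening and baseline tables in SAP 4.6, and the protocol is consistent. That stands: the primary endpoint is not open, and only the SAP wording needs correcting.

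For FVC, SAP 4.17 points to a last-pre-dose value, and the FVC tables sit under that section. It is therefore fairer to say that FVC has conflicting rules across sections, with Visit 1 the only one inside 4.6.1. The FVC outputs are also descriptive. Both points limit the weight, but the SAP still does not say which rule governs.

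For missing values, the rule works in some cases. If Part 1 Day 1 is missing, Day -1 is kept. If Part 2 Day 1 FeNO is missing, nothing valid is displaced. It fails when Part 1 Day -1 is missing, or when exactly one Part 2 Day 1 FEV₁ reading is missing. The documents give no frequency for either. Losing both Day 1 readings should be rare, since randomisation criterion 27 requires a Visit 3 FEV₁.

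The shares and correlations above are assumptions, and one scenario shows no loss. The SAP was also updated for anticipated closure, so 80 per arm may not be reached. The size is therefore illustrative. The faults in the text do not depend on it.

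**Conclusion.** The concern holds on all three counts, and it should be fixed. Every candidate baseline precedes dosing, so the randomised comparison is not biased. For primary FEV₁, the SAP wording must be brought into line with a protocol definition that is clear. For Part 2 FVC, within-arm change tables could include about four to six weeks of pre-dose change, or more if screening or run-in is extended. For the missing-value rule, the loss is small: residual variance rises by 0% to 0.6%, 0% to 2.7% or 0% to 5.4% if 1%, 5% or 10% of patients lack one Day 1 reading. That is at most about 0.5, 2 or 4 of 80 patients per arm. These ranges rest on assumed shares and correlations and a single-timepoint approximation. The precision cost of actually using Visit 1 for FEV₁ is not known from the documents.

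**What to change.** Before unblinding:

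- In SAP 4.6.1, limit the Part 2 Visit 1 clause to the screening and reversibility table.
- State that the mean of the Day 1 readings at -45 and -15 min is the Part 2 in-clinic FEV₁ baseline for SAP 4.11, 4.12.1 and 4.17.5.
- Give Part 2 FVC, and FEV₁/FVC if its change is shown, a Day 1 pre-dose baseline, for example the mean of the same two sessions.
- Note in SAP 4.17 that spirometry follows 4.6.1.
- Replace the non-diary missing-value rule in both Parts: use the mean of whichever defining measurements are available, and go to an earlier value only if all are missing.

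The cost is a few sentences and a check of the derivation code. The Day 1 spirometry is already scheduled, so no new data are needed.
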